# 5. STUDY DESIGN

#### Randomised controlled trial

Pilot data collection 2 weeks from approval of study. 3 months data proper once pilot data has been reviewed and any required changes noted. Data collected from adult inpatients on 10 inpatient wards. Pilot data collection is to identify any problems with the data collection that may arise. If no changes to the protocol are made then this pilot data will be incorporated with the data proper.

Targeted recruitment population: 400 patients total including up to 20 from pilot data. Patients randomised to either intervention (earplugs and eye masks) or control (routine care).

Intervention will be allocated via pre-performed simple randomisation concealed in opaque envelopes with intervention and non-intervention envelopes indistinguishable from one another which will be distributed in batches to each ward engaged in the study.

SleepSure sleep questionnaire will be given to all patients >1 day after recruitment.

## 6. STUDY PARTICIPANTS

### 6.1. Study Participants

Participants will be recruited from adult inpatients who meet the eligibility criteria and admitted to any participating wards in Oxford University Hospitals NHS Foundation Trust.

### 6.2 Inclusion criteria:

Eligible candidates at the point of enrolment must:

- Be 18 years of age
- Be expected to stay in Oxford University Hospitals NHS Foundation Trust for at least one more night
- Be able to understand and use earplugs and eye mask.
- Have basic understanding of English reading and writing.
- Be considered likely to have the Mental Capacity to give consent for use of personal data in the study at the point of filling in the SleepSure Questionnaire (>1 day after recruitment). NB/ Data will not be collected from individuals who are unable to give consent with the filling in of the SleepSure questionnaire.
- Be expected to be able to fill in the SleepSure Questionnaire with or without assistance

# 6.3 The Exclusion Criteria

Candidates will be excluded from the trial if:

- They have or are expected to have an obvious medical contra-indication to the use of earplugs and eye mask at the point of enrolment eg. eye infection, as per clinical judgement of recruiter.
- They are unlikely to benefit from the intervention in the judgement of the recruiter (i.e. individuals who are deaf and blind).

# 7. STUDY PROCEDURES

### 7.1. Recruitment

A ward nurse, part of the direct care team on the ward, will approach potential participants on their arrival on the ward, usually as part of the admission assessment process. If they fulfil the inclusion criteria without exclusion characteristics the patient will be given a brief description of the study and a

Clinical Research Protocol Template version 10.0 CONFIDENTIAL © Copyright: The University of Oxford and Oxford University Hospitals NHS Foundation Trust 2015 Page 8 of 15 Patient Information Sheet; with the permission of the patient any relatives present will also have the study explained and will be given a Patient Information Sheet. They will then be approached by the SleepSure research nurse who will consent and register the patient as a participant.

# 7.2. Informed Consent

Each patient considered eligible will be given a patient information sheet by a nurse on the ward, part of the direct care team. Following this they will be approached by the SleepSure research nurse who will give them a short verbal explanation that will cover:

- The goal of the study (i.e. to study how to improve sleep)
- The trial intervention (i.e. aircraft style earplugs and eye mask)
- The fact that only a 50% chance of getting intervention (random allocation)
- The collection of data (one questionnaire) >1 day after recruitment
- The collection and use of some routine hospital data (falls, use of sleeping tablets, length of stay)
- The option to withdraw consent at any time
- The specific action of having being presented with a SleepSure Questionnaire >1 day after recruitment, which if not filled in will be taken as a refusal of consent for the use of that data in the trial.

A written consent form will be used.

# 7.3. Screening and Eligibility Assessment

As described above, there will be no initial gap between first contact and recruitment.

# 7.4. Randomisation, blinding and code-breaking

Every patient recruited will first be registered by the SleepSure research nurse onto an electronic password-protected Participant ID log in a secure location on the Trust network. This will generate a trial number (e.g. WPH WdA 007 [hospital, ward, number]).

Randomisation:

Using a random number generator performing simple randomisation opaque numbered envelopes will be filled with a piece of paper stating control or intervention with an equal chance of each individual envelope containing a control or an intervention instruction. 50 sealed envelopes will be stacked into a box on each ward, each with a unique identifier number on the outside. When a potential participant is identified the SleepSure research nurse will go to the next envelope in the box and open it to determine if the patient is in the control or intervention arm.

If the patient is allocated to the trial arm, the research nurse will give the patient a set of earplugs and an eyeshade, and explain their use, checking that the patient can use and remove them safely giving instruction as required. The earplugs and eye mask will then be placed into a transparent plastic wallet, labelled with the patient's name, the study and placed within easy reach of the patient.

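### Sections 7.1 and 7.4 conflict on whether the allocation envelope is opened before or after consent and registration, and no step ties the envelope to the patient before it is opened

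*Combined protocol and SAP*

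**What the plan says.** Section 7.1 has a ward nurse approach potential participants on arrival. The SleepSure research nurse follows, "who will consent and register the patient as a participant". Section 7.2 requires a written consent form and a verbal explanation that includes the 50% chance of receiving the intervention.

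Section 7.4 begins: "Every patient recruited will first be registered by the SleepSure research nurse onto an electronic password-protected Participant ID log". The log generates a trial number built from hospital, ward and a running number. On the envelopes, the section says: "50 sealed envelopes will be stacked into a box on each ward, each with a unique identifier number on the outside". The instruction to reveal the allocation is then: "When a potential participant is identified the SleepSure research nurse will go to the next envelope in the box and open it".

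Section 5 adds that the envelopes are opaque and that the two kinds cannot be told apart. Section 11.2 describes the Participant ID log as holding the hospital record number and the anonymous ID. The data list in section 7.6 names neither the envelope number nor the allocated arm.

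**The concern.** Sealed envelopes protect against selection only if the patient is irrevocably in the trial before the envelope is opened. The one sentence that governs opening uses a trigger that, in section 7.1, describes people who have not yet consented. Read on its own, it lets the nurse know the arm while the patient can still be enrolled or passed over.

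This trial has little else to fall back on. The research nurse who obtains consent also registers the patient, opens the envelope, hands over the products and later gives out the questionnaire. Controls are offered nothing (section 13.7), so participants know their arm, and the primary outcome is their own report of sleep. Section 7.5 makes no specific baseline assessment, so the arms cannot be compared or adjusted for sleep before allocation. If the nurse's knowledge of the arm influenced who entered, part of any difference in questionnaire scores would reflect who was enrolled and not what the earplugs and eye masks did.

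**Working it through.** **Order of steps.** The documents state no figure on this point, so the check begins by comparing the texts.

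| Source | Order stated or implied |
|---|---|
| Section 7.1 | Ward nurse approaches a potential participant, then the research nurse consents and registers |
| Section 7.2 | Written consent; the patient is told of a 50% chance, so allocation is still to come |
| Section 7.4, opening paragraph | Each recruited patient is registered first and receives a trial number |
| Section 7.4, opening instruction | Envelope opened once a potential participant is identified |

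The first three rows agree on consent, then registration, with allocation still to come. The fourth uses the term that section 7.1 applies before consent and makes that stage the trigger. The conflict is therefore real, and it falls on the step that reveals the arm.

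**Link between envelope and patient.** The envelope has its own identifier (section 7.4) and the trial number comes from the log (section 7.4). No section says whether the two match. None asks for the sealed envelope to be marked, for its number to be logged before opening, or for opened and unused envelopes to be counted.

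**Would an envelope count reveal a problem?** Inputs: 10 wards (section 5), 50 envelopes per ward (section 7.4), target 400 patients (section 5).

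- Supply: 10 × 50 = 500.
- Surplus: 500 − 400 = 100.

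With about 100 to spare, running out of envelopes would not signal that some had been set aside.

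**Would the arm totals reveal it?** Let f be the assumed fraction of opened control envelopes set aside. To enrol 400:

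- Envelopes opened = 400 / (0.5 + 0.5 × (1 − f))
- Controls enrolled = opened × 0.5 × (1 − f)

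| f (assumed) | Opened | Control : intervention |
|---|---|---|
| 5% | 400 / 0.975 = 410 | 195 : 205 |
| 10% | 400 / 0.95 = 421 | 189 : 211 |
| 20% | 400 / 0.90 = 444 | 178 : 222 |

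Under simple randomisation the size of one arm is binomial (400, 0.5), with standard deviation √(400 × 0.25) = 10 and a central 95% range of 180 to 220. The 5% and 10% cases fall inside that range; the 20% case falls just outside. All three open fewer than 500 envelopes.

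**The case against.** The strongest reply is that the required order is stated and only one noun phrase cuts against it. Section 7.4 says registration comes first, section 7.1 puts consent with registration, and section 7.2 describes allocation as still to come. The envelopes are sealed, opaque, indistinguishable, numbered and taken in order. This largely stands: consent and registration first is the better reading and probably the intended one. It does not remove the contradiction, because the sentence a nurse would act on at the box is the one that departs from that order.

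A reader might infer more than the documents support in four ways.

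- *That the plan prescribes opening before consent.* It does not. That is one literal reading of one sentence, which other text opposes.
- *That the nurse can use a subjective exclusion after seeing the arm.* The criterion "They are unlikely to benefit from the intervention in the judgement of the recruiter" continues with a parenthesis limiting it to people who are deaf and blind, so it is narrow. The recruiter is not defined, and section 7.1 has the criteria applied before the research nurse arrives.
- *That the envelope and trial numbers differ.* The documents do not say. What can be supported is that no linking step is described.
- *That the resulting bias could never be seen or handled.* Gross selection could show in arm totals, as in the 20% case. Age, gender and admission date are collected, and a patient registered first but never allocated would leave a trace in the log.

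Nor do the documents give any basis for a size of bias in the sleep score or for an inflated false-positive rate.

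**Conclusion.** The point holds as an internal contradiction and a missing record-keeping step. Section 7.4 disagrees with itself and with section 7.1 on when the allocation is revealed. Followed literally, its opening instruction allows the arm to be known before enrolment is fixed. Nothing binds the envelope to the patient beforehand or accounts for all 500 envelopes.

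The documents do not allow the effect on the trial result to be quantified. The set-aside fractions are assumed, and the arithmetic takes 400 enrolled with equal allocation probability. It shows only that modest selective enrolment, of the order of 5% to 10% of opened control envelopes, would not stand out in the arm totals. Without a baseline sleep measure there is little else in which to look for it. Nothing here suggests that such selection is intended or likely. The case for acting is that lost concealment cannot be restored afterwards and the protection is nearly free.

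**What to change.** Replace the opening instruction in section 7.4 with wording such as:

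*After written consent is signed and the trial number is generated, the research nurse takes the next envelope in sequence, writes the trial number, date and time on the sealed envelope, enters the envelope number in the Participant ID log, and only then opens it. From that point the patient is counted as randomised.*

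Add a reconciliation, by ward, of all opened and unopened envelopes against the log at the end of recruitment. Because section 11.2 has the log destroyed within 3 months after the study ends, do this before then and keep the ward totals with the anonymised data.

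The final sentence of the new wording matters because section 7.4 checks safe use of the products after opening, in the intervention arm only, and section 7.7 allows removal for ineligibility found later. Counting patients from opening makes any such removals visible by arm.

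The cost is one reworded paragraph, one extra column in a log the trial already keeps, and seconds per patient. The sample size does not change.

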# 7.5. Baseline Assessments

Clinical Research Protocol Template version 10.0 CONFIDENTIAL © Copyright: The University of Oxford and Oxford University Hospitals NHS Foundation Trust 2015 Page 9 of 15 No specific baseline assessment will be made, other than those needed to determine eligibility.

#### 7.6. Subsequent Visits

At the final visit (>1 day after recruitment) the SleepSure research nurse will provide a SleepSure Questionnaire. After discharge the participant's anonymised ID number, age, gender, date of admission, date of discharge, length of stay, number of falls, doses used of zopiclone will be extracted from the notes and recorded by the SleepSure research nurse onto an Excel spreadsheet stored in a secure location on the Trust network with access only via a password-protected computer. The results of the SleepSure questionnaire will also be recorded onto this secure document at this time. (Please see section 11 for more information.)

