### 1. SYNOPSIS

Study Title	SleepSure: a randomised controlled trial to assess the effects of eye masks and earplugs on the quality of sleep for patients in hospital.			
Internal ref. no. / short title	SleepSure: a study aimed at improving sleep for hospital inpatients			
Study Design	Randomised Controlled Trial			
Study Participants	Patients admitted to adult general medical and surgical wards at Oxford University Hospitals NHS Foundation Trust			
Planned Sample Size	400			
Planned Study Period	01 February 2016- 31 January 2017 Pilot data collection 01 February 2016 to 14 February 2015 Recruitment 01 March 2016 – 31 May 2016 (last follow-up 14 June 2016)			
	Objectives	Outcome Measures		
Primary	Do earplugs and eye masks help hospital patients to sleep better?	SleepSure Questionnaire, based on the validated Richards-Campbell Sleep Questionnaire		
Secondary	Does the use of earplugs and eye masks lead to a reduced length of stay, reduced incidence of falls or reduced use of sleep aid medication? How many patients provided with earplugs and an eye mask choose to use them?	Length of stay (days) Number of falls recorded during stay Doses of zopiclone (sleeping tablet) used to help sleep during stay Use of earplugs and eye masks (SleepSure sleep questionnaire)		

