### 4. OBJECTIVES AND OUTCOME MEASURES

Objectives	Outcome Measures	Timepoint(s) of evaluation of this outcome measure (if applicable)
Primary Objective Do ear plugs and eyemasks improve inpatient experience of sleep?	SleepSure sleep questionnaire	Questionnaire given >1 day after recruitment
Secondary Objectives A) How many patients provided with eye masks and earplugs choose to use them?	SleepSure sleep questionnaire	Questionnaire given >1 day after recruitment
B) Does the use of earplugs and eye masks lead to reduced length of stay?	Length of stay data from hospital administration system	After discharge
C) Does the use of earplugs and eye masks lead to reduced use of sleep aid medication?	Drug chart data from electronic records.	After discharge
D) Does the use of earplugs and eye masks lead to a reduced incidence of falls?	Falls data from centrally collated routinely collected information	After discharge

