### 7.8 . Definition of End of Study

The end of study recruitment will be 3 months from the start date. Follow-up data will be collected for a further two weeks. Any patient remaining at that time will be given an outcome questionnaire, and will have their length of stay and other data will be censored at that point (i.e. it will be handled as the date of discharge); the fact of censoring will be noted.

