# **10.1.** Description of Statistical Methods

There will be no interim analysis.

The primary analyses will be to compare the two groups on all items collected, using t-test and Mann-Whitney U tests as appropriate with two-tailed testing (i.e. accepting that harm is also possible). The expectation is that the intervention group will have:

- Better sleep on the questionnaire
- Less use of night sedation over their hospital stay
- Less falls over their hospital stay
- A shorter length of stay

Secondary analyses will investigate:

- Variation between wards on all measures, irrespective of patient group.
- Reported use of and problems with the earplugs and eye masks.

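### Stay, falls and zopiclone are counted over the whole admission, not from randomisation, and unfinished stays are treated as discharges: some power is lost and mean days saved are understated, but no false positives arise

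*Combined protocol and SAP*

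**What the plan says.** **Start of the clock.** The synopsis (section 1) defines the medication outcome as "Doses of zopiclone (sleeping tablet) used to help sleep during stay". Section 10.1 expects "Less use of night sedation over their hospital stay" and words the falls outcome the same way. Section 4 gives "Length of stay data from hospital administration system" as the source for stay. Section 7.6 lists the fields to be taken after discharge, including "date of admission, date of discharge, length of stay, number of falls, doses used of zopiclone will be extracted from the notes". No recruitment or randomisation date is on that list, and no outcome is defined from randomisation.

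**Timing of recruitment.** Under section 7.1 patients are approached when they reach the ward, normally during the admission assessment, and section 7.3 says recruitment follows first contact without delay. Section 6.2 requires one further night to be expected and sets no limit on nights already spent in hospital.

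**Study close.** Section 7.8 says "Follow-up data will be collected for a further two weeks", and the synopsis gives "last follow-up 14 June 2016". For a patient still in hospital then, "length of stay and other data will be censored at that point (i.e. it will be handled as the date of discharge", with the censoring noted. The only tests named, in section 10.1, are comparisons "using t-test and Mann-Whitney U tests as appropriate with two-tailed testing". Section 7.7 records in-hospital deaths, but no rule says how a death enters length of stay.

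**The concern.** Earplugs and an eye mask cannot change nights that were over before they were handed out. Including those nights, with their falls and doses, adds variation that has nothing to do with treatment and pulls any ratio towards one.

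Section 7.8 gives an unfinished stay two incompatible treatments: it is called censored, then given study close as its discharge date. Neither a t-test nor a Mann-Whitney test uses the censoring flag. If the intervention shortens stay, more control stays than intervention stays are cut off, so the gap in mean stay shrinks.

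Shorter stay, fewer falls and less sleep medication are all stated secondary questions, and section 3 cites the daily cost of delayed discharge. Days saved is therefore a figure that readers will want.

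**Working it through.** **The plan's own figure.** Section 10.2 gives 400 patients as a feasibility estimate, with no effect size, SD, alpha or power, so there is nothing to reproduce. For reference, 200 per arm at two-sided 5% (assumed) gives 80% power for (1.960 + 0.842) × √(2/200) = 0.28 SD. Every effect size, distribution and event rate below is an assumption. Section 10.3 drops patients without a questionnaire, so 200 per arm is an upper figure.

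**Step 1: start of the clock, by formula.** Let r be the SD of stay before randomisation divided by the SD after it, and ρ their correlation. The absolute difference is unchanged and the SD grows by √(1 + r² + 2ρr), so

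power = Φ(2.802/√(1 + r² + 2ρr) − 1.960).

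- r = 0.25, ρ = 0: Φ(2.802/1.031 − 1.960) = 77.6%
- r = 0.5, ρ = 0: Φ(2.802/1.118 − 1.960) = 70.7%
- r = 0.25, ρ = 0.3: 72.0%
- r = 0.25, ρ = −0.3: Φ(2.802/0.955 − 1.960) = 83.5%, a gain. Power rises only when ρ < −r/2.

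**Step 2: length of stay, by simulation.** Model A: stay after randomisation is log-normal with mean 6 and log-SD 1, rounded up to whole nights, and 25% shorter under the intervention. Four shapes are used for the earlier nights. Model B: mean 7 days, CV 1, 22% shorter, exponential earlier time. Mann-Whitney power:

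| Mean earlier nights | Model A, average | Model B, from randomisation → whole stay |
|---|---|---|
| 0 | 79% | – |
| 0.5 | 75% | 83.7% → 81.7% |
| 1 | 71% | 83.0% → 79.4% |
| 2 | 64% | 81.4% → 70.5% |

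The loss is 2 to 4 points at half a night, 4 to 8 at one night and 11 to 15 at two. The least favourable of the four shapes in model A, with a quarter of patients transferred from elsewhere, loses 5.7 points at half a night (79.0% to 73.3%).

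The mean difference stays at about 1.5 nights throughout. Rounding up makes the control mean about 6.5, so the relative difference is 1.5/6.5 = 23% with no earlier nights, then 1.5/7 = 21%, 1.5/7.5 = 20% and 1.5/8.5 = 18%.

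**Step 3: counts.** If a fraction f of control events precede randomisation, the observed rate ratio is RR × (1 − f) + f. With RR = 0.65 and f = 10%, 20% or 30% it becomes 0.685, 0.72 or 0.755. At 0.5 events per control patient, power goes from 77.8% to 72.5%, 66.5% and 59.9%.

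- Zopiclone (0.15 doses per night, 40% lower nightly use): the difference stays at 0.39 doses. Mann-Whitney power is 50%, 43%, 38% and 32% with a mean of 0, 0.5, 1 and 2 earlier nights.
- Falls (3, 6 or 10 per 1,000 nights, halved): power is 12%, 17% and 25% from randomisation, against 9%, 14% and 22% with one earlier night.

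**Step 4: study close.** Recruitment from 1 March to 31 May 2016 is 31 + 30 + 31 = 92 days, and follow-up ends 14 days later, so possible follow-up runs from 14 to 106 days, taken as uniform. For a log-normal stay with mean m and log-SD σ, the mean after a cut at c is

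E[min(T, c)] = mΦ(z − σ) + c(1 − Φ(z)), with z = (ln c − ln m + σ²/2)/σ,

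averaged over c. With σ = 1 and a 15% shorter stay (losses from unrounded values):

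| Mean stay, days | Control stays unfinished | True → observed difference, days | Loss |
|---|---|---|---|
| 6 | 1.0% | 0.90 → 0.84 | 6% |
| 7 | 1.4% | 1.05 → 0.97 | 8% |
| 10 | 3.0% | 1.50 → 1.30 | 14% |
| 14 | 5.5% | 2.10 → 1.66 | 21% |

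The loss is 3–13% across these means if σ = 0.8, and 12–30% if σ = 1.2. With a 25% shorter stay, Mann-Whitney power is 79–81% with or without the rule, and t-test power rises from 59–61% to 65–67%. With no treatment effect, both arms are cut by the same rule over the same dates, so the expected difference stays zero.

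**The case against.** The best defence is that nothing here produces a spurious benefit, and that the plan as written points to the mild end. Patients are approached on reaching the ward, so the gap is probably short for most. The plan states no power target and names no ratio. Whole-stay length is a legitimate bed-day measure and suits the cost argument in section 3. At a mean stay of 6–7 days the study-close rule touches about 2 or 3 of 200 control patients (1.0% and 1.4%) and shifts the mean by 0.06 to 0.08 days. A Mann-Whitney test is available for skewed stays, and the censoring is recorded. All of this stands and limits the size of the point.

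Four stronger readings are tempting, and the documents support none of them:

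- That whole-stay counting biases the comparison. Randomisation balances the earlier nights, so the absolute difference is unbiased.
- That the power loss is large. This needs a mean gap of one to two nights, and the documents do not give the gap.
- That the randomisation date is held nowhere. The list in section 7.6 also omits the allocated arm, so it cannot be the full dataset, and staff need the recruitment date to time the questionnaire.
- That the study-close rule invalidates the test of length of stay. It affects an estimated mean difference, which section 10.1 does not name, and leaves a rank test almost unchanged.

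What the defence does not remove is a stated rule that, if stay is shortened, understates days saved, and three secondary outcomes that include time the intervention could not affect.

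**Conclusion.** The point holds at moderate weight. Counting from admission dilutes ratios and, unless earlier and later stay are clearly negatively correlated, costs some power: about 2 to 4 points for length of stay at a mean gap of half a night, and 8 or more only at one to two nights. Under the zopiclone assumptions the loss at half a night is 7 points (50% to 43%). Falls are underpowered from either starting point, so the clock matters little there.

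Handling study close as discharge understates a mean difference by about 6–8% at a mean stay of 6–7 days and 14–21% at 10–14 days, provided that the intervention really shortens stay. The directions follow from the text. The sizes rest on assumed stays, effects and event rates, because the plan gives none.

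The study-close rule can be repaired at analysis because the flag is kept. The randomisation date is better secured now: section 11.2 has the participant ID log destroyed within three months of study end, after which linking back to records could be difficult.

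**What to change.** - **Section 7.6:** add the date of randomisation, and either the dates of falls and zopiclone doses or their counts from that date. Make the from-randomisation figures the analysed outcomes, and keep whole-stay totals as descriptive measures of burden.
- **Section 7.8:** delete the parenthesis that equates study close with discharge, and keep the censoring flag.
- **Section 10.1:** compare time from randomisation to live discharge with a rank test for censored data (Gehan or Peto type), with study close as censoring. State one rule for in-hospital deaths, for example keeping them as never discharged alive (ranked or censored at the longest follow-up), so that a death does not count as a short stay.
- **If days saved are reported:** do not present the raw mean of truncated stays as the full saving. A restricted mean, with its horizon and death rule stated, is an option and not a requirement. Follow-up reaches 14 nights even for a patient recruited on the last day (31 May to 14 June).

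**Cost.** A little more data entry, a few sentences and slightly more analysis, with no extra patient contact. Under the step 4 assumptions with σ = 1, power of the censored rank test is 79–81%, the same as Mann-Whitney, so the gain there is a coherent definition and not sensitivity. A restricted mean omits nights beyond its horizon: 14 nights captures about 34–68% of the full saving over mean stays of 14 down to 6 days and effects of 15–25%.

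### Zopiclone use before randomisation is not recorded, so the unadjusted dose comparison can lose power for objective C and cannot be checked for chance imbalance

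*Combined protocol and SAP*

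**What the plan says.** The Synopsis lists as a secondary outcome "Doses of zopiclone (sleeping tablet) used to help sleep during stay". Section 4 gives the source for objective C as "Drug chart data from electronic records", read after discharge. Section 7.6 names what is taken from the record: trial number, age, gender, admission and discharge dates, and then "length of stay, number of falls, doses used of zopiclone will be extracted from the notes". Prior or regular use of a sleep medicine is not on that list.

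No other section fills the gap. Section 7.5 states: "No specific baseline assessment will be made, other than those needed to determine eligibility". The criteria in Sections 6.2 and 6.3 do not mention sleeping tablets. Section 7.4 describes simple randomisation, "with an equal chance of each individual envelope containing a control or an intervention instruction", with no stratification by prior use. Section 10.1 expects "Less use of night sedation over their hospital stay" in the intervention arm and tests it "using t-test and Mann-Whitney U tests as appropriate with two-tailed testing", with no covariate. Section 10.3 uses everyone who completed the questionnaire and did not withdraw consent, and does not separate existing users from others.

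**The concern.** A patient who already takes zopiclone every night contributes roughly one dose per night in either arm. A patient who starts it in hospital may contribute only a few doses. If the aids work mainly by averting new use, the first group carries little of the signal and can carry much of the variance. Its size in each arm is also left to chance, and the dataset has no item with which to compare the arms on it. Objective C could then return an inconclusive result even though the aids had reduced new sedation. A chance excess of existing users in one arm could also not be told apart from a treatment effect.

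**Working it through.** **The plan's own figure.** Section 10.2 gives 400 participants as a feasibility estimate and says there were no data for a calculation. It states no effect size, SD, power or zopiclone rate, so there is nothing to reproduce. I take 200 per arm. Section 10.3 drops questionnaire non-completers, so this is an upper value.

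**Assumptions, none of them in the documents.** Length of stay is lognormal with median 5 nights and sigma 0.8, in whole nights. A share h of patients are existing users, who take one dose per night in both arms. Among the rest, 20% of controls and 10% of the intervention arm start zopiclone, at about 2 doses each (1 + Poisson(1), capped at the stay). Tests are two-sided at 0.05.

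**Share of doses from existing users.** The mean stay is 5 × exp(0.8²/2) = 6.89 nights. Average new use over the two arms is 15%.

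- h = 2%: 0.02 × 6.89 = 0.138 doses per patient from existing users; 0.98 × 0.15 × 2 = 0.294 from new users; share 0.138/0.432 = 32%.
- h = 5%: 0.344 against 0.95 × 0.15 × 2 = 0.285; share 55%.
- h = 10%: 0.689 against 0.90 × 0.15 × 2 = 0.270; share 72%.

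Most patients have no doses. At h = 5% the proportion with none is 0.95 × 0.85 = 81%.

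**Power by simulation under these assumptions.**

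| Existing users | Mann-Whitney, all, as planned | Rank test stratified by prior use, all | Mann-Whitney, non-users only | t-test, all, as planned | t-test, non-users only |
|---|---|---|---|---|---|
| 2% | 75% | 79% | 80% | 32% | 71% |
| 5% | 66% | 75% | 80% | 17% | 70% |
| 10% | 51% | 65% | 78% | 12% | 67% |

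Repeat runs agreed to within about 4 points. For example, the planned Mann-Whitney test at 5% ranged from 62% to 66%, and the planned t-test at 10% from 9% to 12%. With the rank test, stratifying recovers 79 − 75 = 4, 75 − 66 = 9 and 65 − 51 = 14 points.

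**A second dosing model.** Here the mean stay is about 5 nights, a fraction q of the other controls start zopiclone, starters take a dose on any night with probability r = 0.5, and the aids halve the number of starters. The share of control-arm doses from existing users is h/(h + (1 − h)qr). At q = 20%:

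- h = 2%: 0.02/(0.02 + 0.098) = 17%
- h = 5%: 0.05/(0.05 + 0.095) = 34%
- h = 10%: 0.10/(0.10 + 0.09) = 53%

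Power for the planned tests at q = 20% (t-test / Mann-Whitney) is 58% / 75% with no existing users, 31% / 58% at h = 5%, and 20% / 46% at h = 10%. Among non-users it is 55% / 72% at h = 5% and 53% / 72% at h = 10%. The direction is the same as in the first model, with different sizes.

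**Type I error.** With no true effect and h = 10%, the planned tests reject in 5% of simulated trials.

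**Chance imbalance.** The SD of the between-arm difference in the number of existing users is √(2 × 200 × h(1 − h)). This is 4.4 at h = 5% and 6.0 at h = 10%, giving 95% ranges of about ±8.5 and ±11.8 patients.

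**The case against.** The strongest reply is that randomisation balances prior use on average, that no power was ever claimed for this secondary outcome, and that with about four patients in five at zero doses the rank test is the natural choice under Section 10.1. At 2% to 5% existing users that test loses only a moderate amount. All of this stands, and it limits the point. Section 10.1 does not fix the choice of test, however, so the larger t-test loss remains possible.

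A reader might infer three stronger things that the documents do not support.

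- **That the comparison is biased.** It is not: allocation is random and the type I error is kept.
- **That existing users supply most of the doses and swamp any effect.** The documents give no prevalence. At 2% the share is 32% in one model and 17% in the other, and the rank test keeps most of its power.
- **That the gap can never be repaired.** Section 11.2 keeps the log linking trial number to hospital record number until it is destroyed, within 3 months after the study ends. Until then the chart could be reopened. But no such extraction is planned, and a split chosen after seeing the results would be less credible.

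It is also tempting to make new zopiclone use among non-users the main comparison, because its power is highest. That would narrow objective C, which concerns use of sleep medication among all participants. It would also rest on the aids never reducing existing users' doses, which the power figures here assume and the documents do not show.

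**Conclusion.** The point holds as an avoidable loss of precision on one secondary outcome, together with an imbalance that cannot be checked. With the rank test the avoidable loss is about 4 to 14 percentage points of power as existing users go from 2% to 10%. If the t-test is used, power is about 12% to 32%, against 67% to 71% among non-users. These figures depend on the assumed length of stay, on new use of 20% against 10%, on one dose per night in existing users with no effect of the aids on them, and on a prevalence that the documents do not give. The primary questionnaire result is untouched. This is a cheap improvement, not a flaw that invalidates the trial.

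**What to change.** In Section 7.6, add one yes/no item from the same drug chart: zopiclone or another sleep medicine already in use before randomisation. In Section 10.1, keep all analysed participants in the main zopiclone comparison but stratify it by this item, for example with a van Elteren stratified rank test. Pre-specify one supporting comparison: any new zopiclone after randomisation among patients not using it at randomisation, as a risk difference with 95% confidence interval. That subset is defined by status before randomisation, so the comparison remains randomised.

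The cost is one extra data item from a source already being opened, and two sentences in Section 10.1. The supporting comparison also needs doses to be counted from randomisation. The chart may capture use before admission incompletely, which would weaken the stratification but would not bias the comparison as long as the item reflects status before allocation. No eligibility criterion or prescribing practice changes.
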